2.0 OBJECTIVES AND SCIENTIFIC AIMS

Primary Correlative Objective: Obtain preliminary prospective data on whether mutational load is associated with RECIST 1.1 response to immunotherapy.

Primary Clinical Objective: Obtain prospective data on the overall response Rate (per RECIST 1.1) to 1) nivolumab monotherapy and 2) ipilimumab and nivolumab combination therapy in patients progressing on initial nivolumab monotherapy.

Secondary Clinical Objectives:

1. Evaluate duration of response (DOR), progression free survival (PFS), overall survival (OS), rate of grade 3/4 toxicity.
2. Evaluate ORR, DOR, PFS, OS according to the immune related RECIST criteria.

Secondary Correlative Objectives:

1. Obtain preliminary prospective data on whether neo-antigen score is associated with RECIST 1.1 response to immunotherapy.
2. Compare tumor characteristics (mutation burden, neo-antigen score, PD-L1, TCR repertoire, immune infiltrate) between pre-treatment and on-treatment (optional) tumor biopsies.
3. Evaluate tumor PD-L1 expression across range of mutation burden/predicted neo- antigens.
4. Evaluate TCR repertoire across a range of mutation burdens/predicted neo-antigen scores.
5. Evaluate for the presence of predicted neo-antigen specific T cells in peripheral blood samples.
6. Compare IMPACT assay to whole exome sequencing for the evaluation of patients according to mutation burden.

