- Progressive disease should be confirmed on a second imaging study at least 4 weeks later and should demonstrate at least 10% or greater additional increase in disease burden. Alternatively, if the reviewing radiologist and the treating physician feel that there is unequivocal progression, then the patient may be eligible for crossover after discussion with the principal investigator.
- The patient has not experienced a nivolumab related adverse event(s) leading to permanent discontinuation.
- The patient should have completed at least one cycle of treatment before crossing over the combination treatment. It is not required that the patient receive all scheduled doses of nivolumab during this time; a minimum of 4 doses of nivolumab monotherapy must be given before crossover. Patients may crossover before 4 doses of nivolumab after discussion with the MSK principal investigator.
- The patient must have an ECOG of 0-1.
- In the opinion of the treating investigator, treatment with the combination of ipilimumab and nivolumab represents a reasonable treatment option for the patient.

For patients with bladder cancer, the combination treatment will be 3 mg/kg ipilimumab plus 1 mg/kg nivolumab. The first dose of the combination treatment will be administered at least 2 weeks, but no more than 6 weeks, after the most recent dose of nivolumab. The combination treatment will be administered once every 3 weeks for 4 doses and thereafter, patients will be treated with nivolumab every 2 weeks (240 mg) or every 4 weeks (480 mg) for up to 2 years, if the patient is clinically benefitting, the PI and treating investigator may elect to continue beyond two years.

Schema for Bladder Cancer (prior to Amendment 11)

Schema for Bladder Cancer (after Amendment 11)

See the study flowcharts (Section 10) for a depiction of study event scheduling.

Dosing Adjustments, Delays and Discontinuations

Dosing reductions/adjustments in response to toxicities of nivolumab or ipilimumab are not permitted. Patients who delay or discontinue treatment for toxicities should continue followup as per study calendar (i.e. imaging, study visits, laboratory followup).

Dose Delay Criteria/Criteria to Resume Treatment

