12.0 CRITERIA FOR THERAPEUTIC RESPONSE/OUTCOME ASSESSMENT

Patients are considered evaluable for the primary and secondary endpoints if adequate sequencing data is generated from pre-study biopsy material to determine mutation burden/neo-antigen score.

Responses will be assessed by RECIST 1.1.

Additional clinical endpoints will be evaluated in an exploratory manner.

Duration of Response (DOR) Duration of Response will be determined for each patient with time origin at the first occurrence of confirmed response (CR,PR) until the first occurrence of confirmed progression or date of death if the patient dies due to any causes before progression. Every effort will be made to follow patients for progression after they discontinue the study.

Progression-free Survival (PFS) Progression-free Survival will be determined for each patient with time origin at the start of the treatment (day 1) until the first occurrence of confirmed progression or date of death if the patient dies due to any causes before progression. If a patient does not progress and is still alive, they will be censored on the date of last follow-up. Every effort will be made to follow patients for progression after they discontinue the study.

Overall Survival (OS) Overall survival (OS) will be measured for each patient with time origin at the start of the treatment (day 1) until recorded date of death. If a patient is still alive, they will be censored on the date of last follow-up. Every effort will be made to follow patients for overall survival after they discontinue the study.

Patient Evaluation & Statistics

All patients who receive at least one dose of nivolumab will be evaluated for tumor response (ORR, DOR), including patients who (1) develop rapid symptomatic disease progression, or (2) drop out early due to death or treatment-related toxicities. All patients who received at least one dose of nivolumab will be included in the clinical efficacy analyses of PFS and OS. Kaplan-Meier methodology will be implemented to estimate the median OS and PFS.

Of note, atypical responses are well known to occur in patients treated with immune checkpoint blockade, including early radiographic progression due to immune infiltration followed by subsequent radiographic response and durable clinical benefit. Thus, patients who

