- Dosing interruptions > 6 weeks that occur for non-drug-related reasons may be allowed if approved by the Investigator. Prior to re-initiating treatment in a subject with a dosing interruption lasting > 6 weeks, the Investigator must be consulted. Tumor assessments should continue as per protocol even if dosing is interrupted
- Any adverse event, laboratory abnormality, or intercurrent illness which, in the judgment of the Investigator, presents a substantial clinical risk to the subject with continued nivolumab dosing

Patients who discontinue treatment due to toxicity, as outlined above, will remain eligible for continued followup on study. Followup on study will be modified as described in Study Flowchart 1 and 2.

CRITERIA FOR REMOVAL FROM STUDY

Patients with confirmed disease progression will be removed from the study with limited exceptions outlined below. Progressive disease must be confirmed on a second imaging study at least 4 weeks later and should demonstrate at least 10% or greater additional increase in disease burden. If, based upon the treating physicians judgment, the patient is deriving clinical benefit despite disease progression, treatment beyond progression may be considered provided that (1) the decision is discussed with the MSK and or site PI, who agrees (2) in the opinion of the treating physician, no alternative therapy would offer greater benefit and (3) the treating physician discusses the risks and benefits of continuing on study with the patient, this conversation is documented in the patients' medical records, and the patient wishes to continue treatment.

Removal from study for patients symptomatic progression warranting alternative anti-cancer treatment should be considered in subjects whose overall tumor burden appears to be substantially increased and/or in subjects whose performance status is decreased. These patients will be removed from treatment at the Investigator's discretion in accordance with standard practice.

A patient may withdraw from the study at any time for any reason without prejudice to his/her future medical care by the physician or at the study site.

Patients who are unable or unwilling to comply with study treatment and care plan will be removed from treatment at the Investigator's discretion in accordance with standard practice.

Patient death.

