Patients who receive at least 1 dose of nivolumab and have adequate biopsy material for whole exome sequencing and adequate sequencing data for determination of mutation burden will be considered evaluable for clinical and correlative objectives. Tumor mutation burden and neo-antigen score will be determined for each patient enrolled as described in section Appendix 3. We will perform the same analysis for patients according to their neo-antigen score (as described in Appendix 3). This analysis of the relationship between mutation burden and response rate will be performed for each tumor type independently.

It is anticipated that 4-5 patients per month will be accrued per cohort and accrual will be completed within two years.

Exploratory Endpoints

Patient Evaluation & Statistics for Clinical Endpoints

All patients who received at least one dose of nivolumab will be evaluated for clinical endpoints including tumor response (ORR, DOR, OS and PFS), rate of grade 3/4 toxicity, and survival. Patients who (1) develop rapid symptomatic disease progression, or (2) drop out early due to death will be treated as non responders. Patients who develop early toxicities that require treatment delay or discontinuation will continue to be evaluated for response on study. Kaplan-Meier methodology will be implemented to estimate the median survival time, median progression-free survival, and the PFS and OS rates. Overall survival will be defined as the time from treatment start to death or last follow-up; progression-free survival will be defined as the time from treatment start to the date of progression/death or last follow-up.

Exploratory Tumor and Peripheral Blood Immune Markers

The following endpoints will be evaluated in an exploratory fashion as sample availability permits. Descriptive statistics and graphical measures will be employed. Details related to methods are described in Appendix 3.

- 1. Compare tumor characteristic (mutation burden, neo-antigen score, PD-L1, TCR repertoire, immune infiltrate) between pre-treatment and on-treatment (optional) tumor biopsies**

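### PFS ends at confirmed progression in Section 12 but at any progression in Section 14; the event date and the censoring date are left open, and DOR has no censoring date

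*Combined protocol and SAP*

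**What the plan says.** Section 12 measures PFS with "time origin at the start of the treatment (day 1) until the first occurrence of confirmed progression or date of death". It adds: "If a patient does not progress and is still alive, they will be censored on the date of last follow-up". In Section 14, under the exploratory clinical endpoints, "progression-free survival will be defined as the time from treatment start to the date of progression/death or last follow-up". Neither section refers to the other.

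Confirmation appears where patient handling is described. Section 13, on removal from study: "Progressive disease must be confirmed on a second imaging study at least 4 weeks later and should demonstrate at least 10% or greater" further increase in disease burden. Section 4.2, on crossover: "Progressive disease should be confirmed on a second imaging study at least 4 weeks later", with the same 10% figure, but unequivocal progression is accepted as an alternative. The summary in Section 1.0 asks for a second RECIST 1.1 scan and gives no interval or percentage.

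Sections 12 and 14 share a rule for atypical responses: early radiographic progression that converts to confirmed SD, PR or CR counts as progression-free.

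DOR in Section 12 has "time origin at the first occurrence of confirmed response (CR,PR) until the first occurrence of confirmed progression" or death. No censoring date follows, and Section 14 lists DOR without defining it.

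On status, Section 2 lists as a secondary objective "Evaluate duration of response (DOR), progression free survival (PFS), overall survival (OS), rate of grade 3/4 toxicity", while Section 12 states "Additional clinical endpoints will be evaluated in an exploratory manner".

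**The concern.** The two sections can classify the same patient differently. Consider a radiographic progression that is neither confirmed nor reversed, for example because no second scan was done or because the second scan grew by less than 10%. Under Section 14 this is an event. Read literally, Section 12 has no event until death or a later confirmed progression. The atypical-response rule does not settle such a patient, because there was no conversion.

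Censoring raises a second problem. Section 12 uses the same censoring phrase for PFS as for OS, where any contact showing the patient alive is enough. Section 4.2 gives two routes to contact without imaging before progression: phone calls for patients who decline site visits, and a move to survival follow-up when a patient in toxicity follow-up starts a new therapy. Time without scans could then count as progression-free.

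At stake are the reported Kaplan-Meier PFS and the DOR estimates of a single-arm, open-label cohort. No control group shares the error, and a rule chosen after the data are seen would be hard to defend.

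**Working it through.** **Plan's own figure.** There is none to reproduce. The documents give no expected median, event count or power for PFS or DOR.

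**The passages side by side**

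| Item | Section 12 | Section 14 |
|---|---|---|
| PFS event | confirmed progression, or death | progression, or death |
| Date of a confirmed event (first or second scan) | not stated | not stated |
| Clinical progression without a scan | not stated for PFS | not stated for PFS (the symptomatic-progression rule is written for response) |
| PFS censoring | last follow-up | last follow-up |
| DOR censoring | not stated | not defined |

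**Inputs from the documents.** Scans every 6 weeks to week 24, then every 12 weeks (flowcharts, Section 10.1); 71 bladder patients (Section 14); contact for 4 years, or 208 weeks (Section 4.2).

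**Assumed inputs.** Exponential progression, true median 20 weeks (12 and 30 as checks). Exponential post-progression survival, median 26 or 40 weeks. 10 or 20% of patients set to stop imaging at a uniform time in weeks 4 to 36, with no progression recorded afterwards. 20% of detected progressions unconfirmed at first.

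**1. Complete imaging.** The last scan before week 52 is at week 48, so 1-year PFS is close to 2^(-48/20) = 0.1895. Simulation gives 18.7-19.0%. The true 52-week value is 2^(-52/20) = 0.165; the difference comes from the scan interval alone.

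**2. Section 12, upper bound.** Suppose every unconfirmed progression has an event only at death. The excess is 0.20 × P(progressed by week 48 and alive at week 52). With λ = ln2/20 = 0.03466 and μ = ln2/m:

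P = λ·e^(-52μ)·(1 − e^(-48(λ−μ)))/(λ−μ)

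- m = 26: 0.03466 × 0.250 × 0.319/0.0080 = 0.345, so 0.20 × 0.345 = 6.9 points.
- m = 40: 0.03466 × 0.406 × 0.565/0.01733 = 0.459, so 0.20 × 0.459 = 9.2 points.

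This agrees with the simulated 25.8-28.1%.

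**3. Section 12, with later confirmation.** If each unconfirmed patient has a confirmed progression later on 6-weekly scans (assumed median 8 to 20 weeks), simulation gives 21.2-23.6%, about 2 to 5 points above complete imaging.

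**4. Section 14, some patients leave imaging.** With 10% set to stop (6% leave before progression is found), simulation gives 20.9-21.7%. With 20% (12% leave), it gives 23.1-24.3%. The excess is about 2 to 5 points, and it is an upper bound because no progression is recovered after leaving.

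**5. Other medians.** With true medians of 12 or 30 weeks, the Section 14 excess is 1.9-5.0 points. The Section 12 excess at 20% unconfirmed is 1.7-4.4 (upper bound 6.1-10.0).

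**6. Effect of moving only the censoring date.** Censoring at the last scan while still counting every death lowers 1-year PFS by at most 0.5 points (0.7 with a true median of 30 weeks). Most leavers die within the 208 weeks of contact and keep an event at death, so few are re-censored.

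**7. Precision.** √(0.19 × 0.81/71) = 0.0466, or about 4.7 points.

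**The case against.** Section 14 may simply be shorthand. Section 12 is where outcomes are defined, and its own PFS text drops the word confirmed when it speaks of death before progression and of patients who do not progress. The atypical-response rule is in both sections, which narrows the gap. The crossover and removal rules also largely agree. This is a fair reading, but nothing in the text makes it the rule, and it still does not date the event.

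On censoring, Section 12 promises continued effort to follow patients for progression after they leave the study, and the OS paragraph has a parallel promise for survival. That supports reading last follow-up as follow-up for the endpoint concerned. It states an intention, though, and fixes no date.

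The sizes are all assumed. If half of the progressions after leaving were recovered (also an assumption), the Section 14 excess would fall to about 1 point at 10% leaving and 2 to 3 points at 20%. This objection stands, and the figures should be read as illustration.

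A reader might infer that symptomatic progression without a scan is an immediate event under Section 14. The documents do not establish this, because neither section says whether unscanned clinical progression counts for PFS.

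**Conclusion.** The inconsistency is real on the text and should be corrected before analysis. The event wording differs, the event date is unstated, the censoring date can fall after imaging has stopped, and DOR has no censoring rule. Under the stated assumptions each problem could raise 1-year PFS by about 2 to 5 points, with 7 to 9 as the upper bound for Section 12. That compares with a standard error of about 4.7 points.

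Three stronger readings are not supported:

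- **That reported PFS will be inflated.** The documents give no share of unconfirmed progressions and no rate of leaving imaging. The excess is zero if neither occurs.
- **That leaving imaging shifts the median under Section 14.** A shift can appear when the assumed true median falls on a scan date, such as week 12. It is absent at 11 or 13 weeks, so it is an artefact of the scan grid.
- **That censoring at the last scan cures the problem.** On its own it removes at most about 0.7 points. The event definition and the counts of affected patients matter more.

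PFS and DOR are descriptive here, with no test or sample-size role. The ORR and the AUC analysis are unaffected.

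**What to change.** Put one RECIST 1.1 definition of PFS in Sections 12 and 14:

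- **Event:** first progression, dated at the first scan that shows it unless a later scan refutes it under the existing atypical-response rule; or death.
- **Clinical progression without a scan:** state whether it counts.
- **Censoring:** patients without an event are censored at the last adequate tumour assessment.
- **DOR:** the same progression and censoring rules.
- **Immune-related PFS and DOR (Section 2):** give the matching rule for those criteria.

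Report how many patients left imaging without progression and how many progressions were never confirmed. As an optional sensitivity analysis, censor at the last adequate assessment when death follows a long scan gap or new therapy starts.

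The cost is wording and re-analysis of data already collected. Some patients will be censored earlier, intervals will widen slightly, and reported PFS may be lower.

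Two separate minor points. Use one label, secondary or exploratory, for PFS and DOR. For patients who stop treatment for toxicity, reconcile the imaging schedule under Post-Treatment Follow-up in Section 4.2 (six-monthly or alternate scans) with the dosing-delay text of the same section and with the flowchart footnotes in Section 10.1, which keep the study schedule.

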13.0 CRITERIA FOR TREATMENT DISCONTINUATION OR REMOVAL FROM STUDY

Treatment Discontinuation Criteria

Discontinuation criteria apply for all drug-related adverse events attributed to nivolumab, ipilimumab, or both.

Treatment should be permanently discontinued for the following:

- Any Grade 2 drug-related uveitis or eye pain or blurred vision that does not respond to topical therapy and does not improve to Grade 1 severity within the re-treatment period OR requires systemic treatment
- Any Grade 3 non-skin, drug-related adverse event lasting > 7 days, with the following exceptions for drug-related laboratory abnormalities, uveitis, pneumonitis, bronchospasm, diarrhea, colitis, neurologic adverse event, hypersensitivity reactions, and infusion reactions
 - Grade 3 drug-related uveitis, pneumonitis, bronchospasm, diarrhea, colitis, neurologic adverse event, hypersensitivity reaction, or infusion reaction of any duration requires discontinuation
 - Grade 3 drug-related laboratory abnormalities do not require treatment discontinuation except those noted below
 - Grade 3 drug-related thrombocytopenia > 7 days or associated with bleeding requires discontinuation
 - Any drug-related liver function test (LFT) abnormality that meets the following criteria require discontinuation:
 - AST or ALT > 8 x ULN
 - Total bilirubin > 5 x ULN
 - Concurrent AST or ALT > 3 x ULN and total bilirubin > 2 x ULN
- Any Grade 4 drug-related adverse event or laboratory abnormality, except for the following events which do not require discontinuation:
 - Isolated Grade 4 amylase or lipase abnormalities that are not associated with symptoms or clinical manifestations of pancreatitis and decrease to < Grade 4 within 1 week of onset.
 - Isolated Grade 4 electrolyte imbalances/abnormalities that are not associated with clinical sequelae and a corrected with supplementation/appropriate management within 72 hours of their onset
 - Any dosing interruption lasting > 6 weeks with the following exceptions:
 - Dosing interruptions to allow for prolonged steroid tapers to manage drug-

related adverse events are allowed. Prior to re-initiating treatment in a subject with a dosing interruption lasting > 6 weeks, the Investigator must be consulted. Tumor assessments should continue as per protocol even if dosing is interrupted

- Dosing interruptions > 6 weeks that occur for non-drug-related reasons may be allowed if approved by the Investigator. Prior to re-initiating treatment in a subject with a dosing interruption lasting > 6 weeks, the Investigator must be consulted. Tumor assessments should continue as per protocol even if dosing is interrupted
- Any adverse event, laboratory abnormality, or intercurrent illness which, in the judgment of the Investigator, presents a substantial clinical risk to the subject with continued nivolumab dosing

Patients who discontinue treatment due to toxicity, as outlined above, will remain eligible for continued followup on study. Followup on study will be modified as described in Study Flowchart 1 and 2.

CRITERIA FOR REMOVAL FROM STUDY

Patients with confirmed disease progression will be removed from the study with limited exceptions outlined below. Progressive disease must be confirmed on a second imaging study at least 4 weeks later and should demonstrate at least 10% or greater additional increase in disease burden. If, based upon the treating physicians judgment, the patient is deriving clinical benefit despite disease progression, treatment beyond progression may be considered provided that (1) the decision is discussed with the MSK and or site PI, who agrees (2) in the opinion of the treating physician, no alternative therapy would offer greater benefit and (3) the treating physician discusses the risks and benefits of continuing on study with the patient, this conversation is documented in the patients' medical records, and the patient wishes to continue treatment.

Removal from study for patients symptomatic progression warranting alternative anti-cancer treatment should be considered in subjects whose overall tumor burden appears to be substantially increased and/or in subjects whose performance status is decreased. These patients will be removed from treatment at the Investigator's discretion in accordance with standard practice.

A patient may withdraw from the study at any time for any reason without prejudice to his/her future medical care by the physician or at the study site.

Patients who are unable or unwilling to comply with study treatment and care plan will be removed from treatment at the Investigator's discretion in accordance with standard practice.

Patient death.

